11.1.4 Definitions for Statistical Data Analysis

The following definitions (Table 14) for statistical analyses/presentations will be used:

Table 14: Timepoint Definitions

Term	Definition
Baseline	Baseline is defined as the last available time point prior to T_0 on Day 1. Except for QSU, CO and COHb where the assessment prior to T_0 for each period will be used as a baseline.
T_0	The time of the product use on Day 1 and Day 3, corresponding to the first puffing of CHTP 1.1 M or mCC.

11.1.5 Handling of Dropouts or Missing Data (including outside the limits of quantification)

For questionnaire data total scores and domain or subscale scores may use a certain degree of imputation (by averaging across individual item scores) as detailed in Section 7.3 “Questionnaires”.

In general, values below the lower limit of quantification (LLOQ) will be imputed using 0.5 x lower limit of quantification. For values above the upper limit of quantification (ULOQ), *i.e.*, preceded by a “>”, for example “>xx,” the numerical xx will be used for calculation and reporting in summary tables. The number and percent of values below LLOQ or above ULOQ will be presented in each summary table.

For the calculation of PK parameters, partial dates/times for PK assessments or T_0 will not in general be imputed. For time points recorded in the format hh:mm, instead of hh:mm:ss, the missing information on seconds will be imputed by 30 sec.

For PK concentration data:

- 1) Where there is a missing sample taken at 1 h post-exposure or later
 - and in the subsequent PK sample, nicotine is quantifiable the data will be analysed and reported as planned.
 - And in the subsequent PK sample, nicotine is not quantifiable (BQL) or the missing sample result occurs at 24 h post-exposure AUC_{0-last} will, as well as being analysed and reported as planned, have a sensitivity analysis excluding those subjects.
- 2) Where there is a missing sample before 1 h post-exposure the parameters C_{max} and t_{max} will, as well as being analysed and reported as planned, have a sensitivity analysis excluding those subjects who have a missing sample before 1 h post-exposure.
- 3) Where the sample for the 15 min < T_0 time point is missing AUC_{0-t} will, as well as being analysed and reported as planned, have a sensitivity analysis excluding those subjects who have a missing sample at the 15 min < T_0 time point.
- 4) Where a subject was withdrawn at the 1 h post-exposure or later sample time, the only parameters to be reported would be C_{max} , t_{max} and AUC_{0-t} . All other parameters would be presented as NC (Not calculated) since only a limited partial concentration-

time profile is available and it is not comparable with the same parameters calculated for the other subjects and products and would therefore not be included in the statistical analysis.

- 5) If a subject is withdrawn < 1 h post-exposure, all PK parameters will be presented as NC.

For the PK concentrations below the quantification limit:

- LLOQ values before T_0 are considered as zero.
- LLOQ values after the last quantifiable value are not included in the analysis (e.g., for the calculation of AUC).
- Any other LLOQ value (after T_0 and before the last quantifiable value) would need to be queried and, if confirmed, it will be imputed by $LLOQ/2$.

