**Figure 1 Study Flow Chart****2) The Investigational Period (from Day -2 to Discharge):**

The Investigational period will consist of 2 periods (Period 1, Period 2) with each period consisting of approximately 48 to 57 hours smoking abstinence and 1 day of single product use.

Period 1: From Day -2 to Day 1. After Day 1 product use, the subject will start his/her washout for period 2

Period 2: From Day 2 to Day 3. The products should be used at the same time (within 1 hour) on Day 1 and Day 3

48 eligible, healthy smoking subjects will be randomized to one of 2 sequences:

Table 1 Definition of Randomization Sequences

Sequence	Sample Size
1. CHTP 1.1 M then mCC	24
2. mCC then CHTP 1.1 M	24

Each sex and smoking strata (International Organization for Standardization [ISO] nicotine levels ≤ 0.6 mg vs. >0.6 to 1.0 mg) will have a quota applied to ensure they represent at least 40% of the study population for each Sequence (Sequence 1 and Sequence 2).

Subjects who do not complete the study after randomization will not be replaced.

Subjects will be discharged from the investigational site in the morning of Day 4 after performance of Discharge assessments.

3) The Safety Follow-up Period (from Discharge until Day 11):

A 7-day safety follow-up will be done for the recording of spontaneously reported AEs and SAEs (passive surveillance) and the active follow-up by the investigational site of AEs/SAEs ongoing at Discharge. Any AE will in general be followed-up until resolved, stabilized (*i.e.*, no worsening of the event), or until a plausible explanation for the event has been found.

The end of study for the subject is defined as the date of completion or discontinuation on Subject status form completed. AEs/SAEs not resolved or not stabilized at EOS are to be recorded as ongoing at EOS.

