6.3 Product Allocation and Blinding

6.3.1 Methods of Assigning Subjects to Treatment Sequences

Randomization to product exposure sequence will be done through [REDACTED].

Each sex and each of the smoking level (ISO nicotine levels ≤ 0.6 mg and >0.6 to 1 mg) will have a quota applied to ensure they represent at least 40% of the total study.

In particular, the maximum number of subjects having the same sex or nicotine level value will be limited to 28.

The randomization of the planned sample size of 48 subjects will be ensured by applying quota to the number of subjects per each sequence (24 subjects).

Subjects will be randomly assigned to one of the two product exposure sequences by means of a permuted-block schema. Block size and other randomization details will be available in the randomization plan.

The randomization plan will be generated by an independent statistician and none of the CRO and sponsor staff, Investigators, and study subjects will have any access to the randomization schema prior to randomization.

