11.6.3 Supportive/Sensitivity Analysis

To better understand the impact of the higher than expected T_0 values, an analysis of the PK parameters will be performed as described above, however the data for subjects with their T_0 value $>5\%$ of their C_{max} value will be excluded from the analysis. To support the interpretation of the PK analysis, the values of nicotine concentration greater than BLOQ before T_0 will be listed together with any PK parameters excluded from the analysis. Listings will be presented by PK parameter, sequence, period and study date.

Sensitivity analysis will be conducted on the C_{max} and $AUC_{(0-last)}$ endpoints for the PK population should there be 20% or more missing PK parameter values. This analysis is conducted on all the available PK parameters and subjects will be excluded from the analysis if 20% or more of their PK parameter values are missing. The analysis will be conducted in the natural log scale using mixed effects ANOVA model including period, sequence, and product exposure as fixed effects and subject within sequence as a random effect. Point and 95% interval estimates of the ratios will be back-transformed by exponentiation and tabulated.

Sensitivity analysis will be conducted following the model described in 11.6.1 “Primary Analyses” in case of missing data as described in Section 11.1.5 “Handling of Dropouts or Missing Data (including outside the limits of quantification)”:

- 1) Where there is a missing sample taken at 1 h post-exposure or later and in the subsequent PK sample, nicotine is not quantifiable (BQL) or the missing sample result occurs at 24 h post-exposure AUC_{0-last} will, as well as being analysed and reported as planned, have a sensitivity analysis excluding those subjects.
- 2) Where there is a missing sample before 1 h post-exposure the parameters C_{max} and t_{max} will, as well as being analysed and reported as planned, have a sensitivity analysis excluding those subjects who have a missing sample before 1 h post-exposure.
- 3) Where the sample for the $15 \text{ min} < T_0$ time point is missing AUC_{0-t} will, as well as being analysed and reported as planned, have a sensitivity analysis excluding those subjects who have a missing sample at the $15 \text{ min} < T_0$ time point.

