In case any time information is imputed for the computation of PK parameters as described in Section 11.1.5 “Handling of Dropouts or Missing Data (including outside the limits of quantification)” in any PK population, the median t_{max} for CHTP 1.1 M will be calculated following the imputation of missing time data by 0 sec and 30 sec. If the difference between the two median t_{max} is larger than 5%, a supportive analysis will be conducted by repeating the analyses described in Section 11.6.1 “Primary Analyses” and 11.6.2.1 “Pharmacokinetics” on the t_{max} , $AUC_{(0-last)}$, and $AUC_{(0-t)}$ endpoints estimated by means of the imputation of missing time by 0 sec.

The data will be presented in the below outputs:

TFL number	Title
TABLES	
Table 15.2.4.2.1	Analysis of Pharmacokinetic Parameters of Nicotine: sensitivity analysis: missing data - PK Population
Table 15.2.4.2.2	Analysis of Pharmacokinetic Parameters of Nicotine: sensitivity analysis: quantifiable predose concentrations - PK Population
Table 15.2.4.2.3	Analysis of Pharmacokinetic Parameters of Nicotine: sensitivity analysis: missing concentrations – PK Population
Table 15.2.4.3	Analysis of Pharmacokinetic Parameters of Nicotine by Zero Sec Imputation – PK Population

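### Do the below-LLOQ rules for nicotine concentrations leave the by-time-point geometric means and the topline profile undefined or biased?

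*SAP*

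**What the plan says.** Section 11.1.5 contains two sets of rules.

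- **General default.** Ordinarily, "values below the lower limit of quantification (LLOQ) will be imputed using 0.5 x lower limit of quantification". The same paragraph adds: "The number and percent of values below LLOQ or above ULOQ will be presented in each summary table".
- **PK concentrations.** BLQ values before T0 "are considered as zero". For the tail of the profile, "LLOQ values after the last quantifiable value are not included in the analysis", with the calculation of AUC as the only example. A BLQ value between T0 and the last quantifiable value is queried and, if confirmed, set to LLOQ/2.

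Section 11.6.2.1 has nicotine concentrations summarised like the PK parameters and split by sample time. Section 11.1.3 adds the geometric mean and CV to PK parameter summaries. A geometric mean profile with 95% CI is also planned (Figure 15.1.2.1). Section 12.3 places Table 15.2.4.5 and Figure 15.1.2.1 among the topline outputs. None of these sections names a BLQ rule.

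**The concern.** The second set of rules is introduced for PK concentrations in general, and its AUC example is only an example. A literal reader could therefore carry it into the concentration tables and the profile figure. Two things would go wrong.

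- **Before T0.** A zero has no logarithm. One such value makes the geometric mean zero and leaves no log-scale interval. If software drops the zeros, only subjects with residual nicotine remain. BLQ values are likely here, because each period includes "approximately 48 to 57 hours smoking abstinence". Section 11.6.3 also treats quantifiable pre-use values as exceptions: it lists "the values of nicotine concentration greater than BLOQ before" T0 and plans a table titled "sensitivity analysis: quantifiable predose concentrations".
- **At 24 h.** This is the last sample, so any BLQ value there lies after the last quantifiable one. Omitting all of them means the geometric mean cannot fall below the LLOQ.

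Two programmers could then deliver different versions of a topline figure that compares the two products by eye.

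**Working it through.** The SAP states no figure on this point to reproduce. The check is what each reading produces, and then which reading the text supports.

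**1. Where the rule sets differ.** Both give LLOQ/2 for a confirmed BLQ value between T0 and the last quantifiable sample. They differ only before T0 (zero against LLOQ/2) and in the tail (omitted against LLOQ/2).

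**2. Pre-T0, zero rule taken literally.** The chance of at least one zero among n subjects, each with BLQ probability q, is 1 − (1 − q)^n. The SAP gives no q, so 5% is an assumption. Section 8 gives n = 48. Section 6.3.1 says "the maximum number of subjects having the same sex or nicotine level value will be limited to 28", so the smallest full stratum is 48 − 28 = 20.

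- n = 48: 1 − 0.95^48 = 91%
- n = 20: 1 − 0.95^20 = 64%

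As an example, take 40 of 48 values BLQ and 8 at 1.5 × LLOQ. The zero rule gives a geometric mean of 0. LLOQ/2 gives exp[(40 ln 0.5 + 8 ln 1.5)/48] = exp(−0.510) = 0.60 × LLOQ.

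**3. 24 h, omission taken literally.** The SAP gives no LLOQ, BLQ rate or between-subject CV for late samples. The 60% in Section 8 is a within-subject CV for Cmax, which is a different quantity. Assume lognormal concentrations, true geometric mean 1, BLQ fraction p and CV 60% (range 40 to 100%).

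- σ = √ln(1 + CV²) = √ln 1.36 = 0.5545
- z = Φ⁻¹(p), λ = φ(z)/(1 − p), LLOQ = exp(σz)
- Omission: ratio to the true geometric mean = exp(σλ)
- LLOQ/2: ratio = exp[p ln(LLOQ/2) + (1 − p)σλ]

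At p = 0.10, λ = 0.1755/0.90 = 0.1950, so omission gives exp(0.1081) = 1.11. At p = 0.50, λ = 0.3989/0.50 = 0.7979, so omission gives exp(0.4424) = 1.56 and LLOQ/2 gives exp(−0.3466 + 0.2212) = 0.88.

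| BLQ | Omission, CV 60% (40%; 100%) | LLOQ/2, CV 60% (40%; 100%) |
|---|---|---|
| 10% | 1.11 (1.08; 1.18) | 0.96 (0.95; 0.97) |
| 25% | 1.26 (1.18; 1.42) | 0.91 (0.89; 0.95) |
| 50% | 1.56 (1.36; 1.94) | 0.88 (0.82; 0.99) |

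At 2% BLQ, omission gives only 1.02 to 1.04. In 40,000 simulated samples of 48, the nominal 95% interval covered the true geometric mean about 70, 5 and 0% of the time under omission, at 10, 25 and 50% BLQ. Under LLOQ/2 it covered 94, 85 and 71% at CV 60%, and 91, 71 and 31% at CV 40%.

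**4. Which reading the text supports.**

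- The numbered PK items just before the disputed rules all concern parameters: AUC(0-last), Cmax, tmax, the partial AUC, and when a parameter is not calculated.
- The disputed rules sort values as before T0, after the last quantifiable value, or in between. That is how a single subject's profile is prepared for non-compartmental analysis. It is not how one time point is summarised across subjects.
- Sections 11.1.3 and 11.6.2.1 require a geometric mean. The zero rule makes that statistic degenerate, so it cannot sensibly have been written for it.
- The LLOQ/2 paragraph is the one that refers to summary tables.

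Read together, zero and omission belong to parameter derivation, and LLOQ/2 belongs to the summaries. On that reading both problems disappear.

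**The case for a change.** The best case for a change is that a specific rule normally displaces a general one. The specific rule here is introduced for PK concentrations without limit, and its AUC example is not exclusive. The outputs are topline, and the required BLQ counts apply to tables, not to the figure. Omission at 24 h would leave no visible sign on the plot. If the two products had different BLQ rates, the visual contrast would shift: with an assumed geometric SD of 2 and BLQ rates of 60% (CHTP 1.1 M) and 30% (mCC), a true ratio of 0.58 would appear as 0.81 under omission and 0.60 under LLOQ/2. One sentence would close the gap.

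Part of this stands. No sentence assigns a rule to the summaries, and the figure carries no required count. But the displacement argument leads to a statistic that cannot be computed before T0, which would send a programmer back to the default stated in the same section. A zero or blank first point would be noticed, and nothing in the SAP tells anyone to drop zeros silently. Selection at 24 h would show in Table 15.2.4.5 and its strata through the BLQ n and %. Section 3 leaves the detailed description of outputs to a separate shells document, which is not at hand; figure annotation is the kind of detail left there. The sentence would largely restate a default that the SAP already has, and that default is itself imperfect when BLQ values are common.

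**Conclusion.** No change to the plan is needed. The scope of a rule is not spelled out, but the context points to one workable reading, and analysts can be expected to adopt it: zero and omission for deriving parameters, LLOQ/2 for concentration summaries.

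The stakes are small. Only descriptive outputs are involved. Cmax, AUC(0-last) and the planned models do not depend on the answer, because the specific rules plainly cover parameter derivation. The pre-T0 median and quartiles stay defined on either reading. Section 5.4.1 states that no hypothesis is tested, and Section 11.1.7 that no claim rests on individual intervals.

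The inflation of 1.11 to 1.56 times and the loss of coverage arise only on the disfavoured reading, at assumed BLQ rates of 10 to 50% and an assumed CV of 60%. At 2% BLQ the inflation is 1.02 to 1.04. Nothing in the SAP shows which rate applies. The judgement would differ only if the output specifications expressly carried the zero and omission rules into the geometric mean summaries.

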11.1.5.1 Insufficient Data for Analysis/Presentation

If there are no values/event at the general value then the break out should not be presented. For example if the number of related AEs is zero then no presentation by severity of related events at the single level will be produced.

Some of the TFLs may not have sufficient numbers of subjects or data for presentation. If this occurs, the blank TFL shell will be presented with a message printed in the center of the table, such as, "No serious adverse events occurred for this study."

Stratified summaries by sex or nicotine levels will not be presented if less than 4 subjects are available in one sex or nicotine levels strata.

11.1.6 Handling of Unplanned Data

Unscheduled post-product use assessments will be excluded from the summary statistics. Unscheduled assessments will be labelled as unscheduled in the listings and mapped to the study day using the date of the study day until midnight.

11.1.7 Multiple Comparisons / Multiplicity

No formal adjustment of the test-wise alpha level for multiple testing is necessary, as no claim will be made based on the outcome of the individual CI values.

11.2 Disposition of Subjects

The number and percent of subjects will be summarized for the following categories: subjects screened, screening failed, enrolled subjects, enrolled and not randomized, randomized subjects, completed, and discontinued.

Inclusion and exclusion criteria will be listed as to whether the subjects have met or not met the criteria by sequence, subject, and study day (Screening and Admission).

Subjects in the Safety and PK populations will be displayed by sequence and overall.

All subjects who fail to complete the study will be categorized by their primary reason for discontinuation and summarized by sequence and overall. Disposition of subjects and reasons for withdrawal will also be summarized separately. Supportive listings will be provided.

The number and percent of randomized subjects with protocol deviations and the number of protocol deviations will be summarized by sequence and overall, broken down by main deviation category (major/minor) and sub-categories. Subjects will be counted once per deviation category, and can be counted for more than one deviation category.

Supportive listing will be provided, including any additional comments for tests that are not performed to be included on the listings of individual data.

The data will be presented in the below outputs:

TFL number	Title
TABLES	
15.2.1.1	Summary of Subject Disposition – Screened Population
15.2.1.2	Summary of Reasons for Discontinuations – Randomized Population
15.2.1.3	Summary of Protocol Deviations – Safety Population
LISTINGS	
15.3.1.1	Listing of Inclusion/Exclusion Criteria
15.3.1.7	Listing of Subject Disposition and Assignment to Analysis Sets
15.3.2.3	Listing of Subjects and Observations Excluded from the PK Population and PK Analysis
15.3.1.11	Listing of Protocol Deviations
16.1.7	Listing of Randomization Scheme and Codes

11.3 Demographics and Other Baseline Characteristics

Demographic and baseline characteristics will be summarized for the Safety and PK populations, and listed for the Safety population.

The demographic variables age, sex, ethnicity, body weight, height and BMI will be summarized by sequence and overall for the Safety population.

Demographics will be tabulated overall and by the two stratification factors (sex and mCC nicotine level at Admission) for the PK populations, as specified in Section 11.1.1 “Stratified Presentation”.

No inferential analyses will be presented for the demographic and baseline characteristics.

The data will be presented in the below outputs:

TFL number	Title
TABLES	
15.2.1.4.1	Summary of Demographics and Other Baseline Characteristics – Safety Population
15.2.1.4.2	Summary of Demographics and Other Baseline Characteristics – PK Population
15.2.1.4.2.1	Summary of Demographics and Other Baseline Characteristics by Sex – PK Population
15.2.1.4.2.2	Summary of Demographics and Other Baseline Characteristics by Nicotine Level –PK Population
LISTINGS	
15.3.1.6	Listing of Demographics

11.3.1 CYP2A6 Activity at Admission

CYP2A6 activity will be calculated as the metabolite molar ratio of trans 3' hydroxycotinine and COT measured at Day-3 in plasma, as described in Section 7.2 "Biomarkers".

Data will be listed and summarized as reported in Section 11.3 "Demographics and Other Baseline Characteristics".

The data will be presented in the below outputs:

TFL number	Title
TABLES	
15.2.1.4.1	Summary of Demographics and Other Baseline Characteristics – Safety Population
15.2.1.4.2	Summary of Demographics and Other Baseline Characteristics – PK Population
15.2.1.4.2.1	Summary of Demographics and Other Baseline Characteristics by Sex – PK Population
15.2.1.4.2.2	Summary of Demographics and Other Baseline Characteristics by Nicotine Level – PK Population
LISTINGS	
15.3.1.10	Listing of CYP2A6 Activity – Safety Population

11.3.2 FTND Questionnaire at Screening

FTND score value and the number and percentage of subjects in each category (mild/moderate/severe) will be presented. Data will be listed and summarized as reported in Section 11.3 "Demographics and Other Baseline Characteristics".

The data will be presented in the below outputs:

TFL number	Title
TABLES	
15.2.1.4.1	Summary of Demographics and Other Baseline Characteristics – Safety Population
15.2.1.4.2	Summary of Demographics and Other Baseline Characteristics – PK Population
15.2.1.4.2.1	Summary of Demographics and Other Baseline Characteristics by Sex – PK Population
15.2.1.4.2.2	Summary of Demographics and Other Baseline Characteristics by Nicotine Level – PK Population
LISTINGS	
15.3.1.9	Listing of Fagerström Test for Nicotine Dependence Results

11.3.3 Current Cigarette and Smoking Characteristics

The following smoking characteristics at Admission (Day -3) will be summarized and listed as specified in Section 11.3 “Demographics and Other Baseline Characteristics”: ISO tar yield (continuous and categorized as 1-5 mg, 6-8 mg, 9-10 mg and >10 mg), ISO nicotine level (continuous and categorized as ≤ 0.6 mg, > 0.6 to ≤ 1 mg, and > 1 mg), and number of mCCs smoked on a daily basis during the previous 4 weeks (categorized as < 10 cig/day, 10-19 cig/day and > 19 cig/day).

Current mCC brand(s) smoked by the subject will be summarized and listed by sequence at Admission (Day -3) for the safety population. This will include brand name(s), and ISO nicotine and tar yields. The current mCC brand collected at Screening Visit will be listed only.

Smoking history, including whether subjects have smoked for at least the last three consecutive years, number of mentholated cigarettes smoked on average during the previous 4 weeks, and willingness to interrupt smoking up to 6 days will be listed by sequence at Screening and Admission (Day -3) Responses to planning to quit smoking during the next 3 months will be listed at Screening.

Data will be listed and summarized as presented in the below outputs:

TFL number	Title
TABLES	
15.2.1.4.1	Summary of Demographics and Other Baseline Characteristics – Safety Population
15.2.1.4.2	Summary of Demographics and Other Baseline Characteristics – PK Population

TFL number	Title
15.2.1.4.2.1	Summary of Demographics and Other Baseline Characteristics by Sex – PK Population
15.2.1.4.2.2	Summary of Demographics and Other Baseline Characteristics by Nicotine Level – PK Population
15.2.1.5	Summary of Current Cigarette Brands at Admission – Safety Population
LISTINGS	
15.3.1.2	Listing of Current Cigarette Brands
15.3.1.3	Listing of Smoking History
15.3.1.4	Listing of Product Test, Willingness to interrupt smoking up to 6 days, Willingness to Quit Smoking,

